#### **8.3.5 ADVERSE EVENT REPORTING**

A member of the study staff shall complete a summary report or log of all AEs and submit to the UCSD Office of IRB Administration at the time of study annual renewal or closeout.

---

#### **8.3.6 SERIOUS ADVERSE EVENT REPORTING**

The study investigator shall complete an SAE Form and submit to the UCSD Office of IRB Administration as soon as possible, but no later than 10 working days after the investigator first learns of the effect.

---

#### **8.3.7 REPORTING EVENTS TO PARTICIPANTS**

In the event of an SAE determined to be related to study procedure, participants will be informed after IRB review of the event. Upon IRB acknowledgement and study team fulfillment of any protocol changes, participants will be informed via a consent form addendum or a new version of the consent form. Participants will be given the choice to withdraw from the study or sign the new consent and continue.

---

#### **8.3.8 EVENTS OF SPECIAL INTEREST**

Not applicable.

---

### 8.3.9 REPORTING OF PREGNANCY

Pregnancy is not considered an AE for this study: there is no prohibition against pregnancy following cryoneurolysis and study participants will not be counselled regarding subsequent birth control.

## 8.4 UNANTICIPATED PROBLEMS

---

### 8.4.1 DEFINITION OF UNANTICIPATED PROBLEMS (UP)

The Office for Human Research Protections (OHRP) considers unanticipated problems involving risks to participants or others to include, in general, any incident, experience, or outcome that meets all of the following criteria:

- Unexpected in terms of nature, severity, or frequency given (a) the research procedures that are described in the protocol-related documents, such as the Institutional Review Board (IRB)-approved research protocol and informed consent document; and (b) the characteristics of the participant population being studied;
- Related or possibly related to participation in the research (“possibly related” means there is a reasonable possibility that the incident, experience, or outcome may have been caused by the procedures involved in the research); and
- Suggests that the research places participants or others at a greater risk of harm (including physical, psychological, economic, or social harm) than was previously known or recognized.

---

### 8.4.2 UNANTICIPATED PROBLEM REPORTING

The investigator will report unanticipated problems (UPs) to UCSD Office of IRB Administration. The UP report will include the following information:

- Protocol identifying information: protocol title and number, PI’s name, and the IRB project number;
- A detailed description of the event, incident, experience, or outcome;
- An explanation of the basis for determining that the event, incident, experience, or outcome represents an UP;
- A description of any changes to the protocol or other corrective actions that have been taken or are proposed in response to the UP.

To satisfy the requirement for prompt reporting, UPs will be reported using the following timeline:

- UPs that are serious adverse events (SAEs) will be reported to the IRB within 10 days of the investigator becoming aware of the event.
- Any other UP will be reported to the IRB within 30 days of the investigator becoming aware of the problem.
- All unanticipated events and adverse events will be reported to the specific center's Institutional Review Board (IRB), the primary supervising IRB (University of California San Diego), the study Data and Safety Monitoring Board (DSMB), and the Army Human Research Protections Office. The adverse event and unanticipated event profile will be discussed at monthly executive committee video-conference meetings.

#### 8.4.3 REPORTING UNANTICIPATED PROBLEMS TO PARTICIPANTS

In the event of a UP determined to be related to study procedure, participants will be informed after IRB review of the event. Upon IRB acknowledgement and study team fulfillment of any protocol changes, participants will be informed via a consent form addendum or a new version of the consent form. Participants will be given the choice to withdraw from the study or sign the new consent and continue.

### 9 STATISTICAL CONSIDERATIONS

#### 9.1 STATISTICAL HYPOTHESES

**Statistical analysis:** Continuous, normally distributed data will be reported as mean  $\pm$  standard deviation. Nonparametric continuous or categorical data will be reported as median [10th-90th percentiles] or percent, as appropriate. Comparisons of independent samples will be performed using Student's t-test for parametric continuous variables or Mann-Whitney U test for nonparametric or categorical variables. The Chi Square test and Fisher's Exact test will be used for differences in proportions, as appropriate.  $P < 0.05$  will be considered statistically significant for the primary outcome. Results of comparisons in secondary outcomes will be interpreted as suggestive, requiring confirmation in a future trial before considering them as definitive.

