Objectives:	
The ultimate objective of the proposed research study is to demonstrate feasibility and estimate the treatment effect of using cryoanalgesia as a treatment for intractable phantom limb pain following a trans-femoral (above-knee) amputation to assist in determining the required sample size of a subsequent definitive clinical trial.
 
Primary Specific Aim: To test the influence of a cryoanalgesia treatment as compared to sham/placebo on the intensity of existing, intractable phantom limb pain resulting from an above-knee amputation.
 
Hypothesis 1: Phantom limb pain intensity will be decreased relative to baseline 1 month following a cryoneurolysis procedure (as measured by the Numeric Rating Scale within the Brief Pain Inventory).
 
Secondary Specific Aim: To test the influence of a cryoanalgesia treatment as compared to sham/placebo on the quality of life for individuals with intractable phantom limb pain resulting from an above-knee amputation.
 
Hypothesis 2a: Perception of well-being will be improved 1 month following one cryoneurolysis procedure (as measured with the Patient Global Impression of Change Scale).
 
Hypothesis 2b: Physical and emotional functioning will be improved relative to baseline 1 month following one cryoneurolysis procedure (as measured with the Interference Subscale of the Brief Pain Inventory).

[figure not shown]
Endpoints:	Hypothesis 1: Phantom limb pain intensity will be decreased relative to baseline 1 month following a cryoneurolysis procedure (as measured by the Numeric Rating Scale within the Brief Pain Inventory).																																																																																																																																																																																													
	Hypothesis 2a: Perception of well-being will be improved 1 month following one cryoneurolysis procedure (as measured with the Patient Global Impression of Change Scale).																																																																																																																																																																																													

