### 3 OBJECTIVES AND ENDPOINTS

OBJECTIVES	ENDPOINTS	JUSTIFICATION FOR ENDPOINTS
Primary		
To estimate the analgesic effect of cryoneurolysis on intractable post-amputation (trans-femoral) phantom limb pain 1 month post-treatment	Phantom limb pain intensity will be significantly decreased relative to baseline pain 1 month following a cryoneurolysis procedure (as measured by the Numeric Rating Scale within the Brief Pain Inventory).	Pain negatively influences physical and emotional functioning.
Secondary		
To estimate the analgesic effect of cryoneurolysis on intractable post-amputation (trans-femoral) phantom limb pain at various time points post-treatment (Days 1, 7, and Months 2, 3, 4, and 12)	Phantom limb pain intensity will be significantly decreased relative to baseline pain at various time points following a cryoneurolysis procedure (as measured by the Numeric Rating Scale within the Brief Pain Inventory).	Pain negatively influences physical and emotional functioning.
To estimate the analgesic effect of cryoneurolysis on intractable post-amputation (trans-femoral) residual limb pain at various time points post-treatment (Days 1, 7, and Months 1, 2, 3, 4, and 12)	Residual limb pain intensity will be significantly decreased relative to baseline pain at various time points following a cryoneurolysis procedure (as measured by the Numeric Rating Scale within the Brief Pain Inventory).	Pain negatively influences physical and emotional functioning.
To estimate the effect of cryoneurolysis on the perception of well-being in patients with intractable post-amputation (trans-femoral) phantom limb pain	The perception of well-being as measured with the Patient Global Impression of Change Scale will be improved at various time points following a cryoneurolysis procedure (Days 1, 7, and Months 1, 2, 3, 4, and 12)	Global perception of well-being is indicative of patients' own perception of their life status.
To estimate the effect of cryoneurolysis on the physical and emotional functioning of patients with intractable post-amputation (trans-femoral) phantom limb pain	The physical and emotional functioning of patients will be improved at various time points following a cryoneurolysis procedure relative to baseline as measured with the Brief Pain Inventory Interference Subscale(Days 1, 7, and Months 1, 2, 3, 4, and 12)	Pain negatively influences physical and emotional functioning.

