## 4 STUDY DESIGN

### 4.1 OVERALL DESIGN

The study is a single-center, randomized, participant- and observer-masked, active-controlled, parallel-arm, optional crossover, human-subjects, post-market clinical pilot study to investigate the use of ultrasound-guided percutaneous cryoneurolysis to treat phantom limb pain following a trans-femoral (above-knee) amputation. Participants with intractable phantom limb pain will be randomly allocated to one of two possible treatment groups: cryoneurolysis (experimental) or sham (control). The primary outcome measure is the change in the phantom limb pain intensity from baseline 1 month following the procedure as measured by the Numeric Rating Scale within the Brief Pain Inventory.

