## 8 STUDY ASSESSMENTS AND PROCEDURES

### 8.1 EFFICACY ASSESSMENTS

**Outcome measurements.** We have selected outcome measures that have established reliability and validity, with minimal inter-rater discordance, and are recommended for chronic pain clinical trials by the Initiative on Methods, Measurement, and Pain Assessment in Clinical Trials (IMMPACT) consensus statement. ***The primary end point will be the difference in average daily phantom pain intensity at baseline and 1 month following the initial intervention (measured with the NRS as part of the Brief Pain Inventory).*** The primary analyses will compare the two treatments (inter-subject comparisons) during the initial treatment period in which half of the subjects will receive active cryoneurolysis and the other half a sham/placebo treatment. Endpoints will be evaluated at baseline and post-treatment (Day 0), Days 1 and 7; and Months 1, 2, 3, 4, and 12, (Table 1). These same time points through month 4 will be evaluated following the optional second (crossover) treatment.

The questionnaire will differentiate among multiple dimensions of limb pain:

***Residual limb (“stump”) pain:*** painful sensations localized to the portion of limb still present.

***Phantom limb sensations:*** non-painful sensations referred to the lost body part.

***Phantom limb pain:*** painful sensations referred to the lost body part.

Each type of pain/sensation will be defined for subjects immediately prior to questionnaire application at each time point, and subjects will be instructed to specifically address phantom limb pain when responding to the various questions. In addition, since there is a strong correlation between phantom and residual limb pain, we will specifically inquire about both types of pain. Each time the questionnaire is applied, subjects will be instructed to respond for the previous 3 days (e.g., worst pain during the previous 3 days) because studies have suggested that patients have “increasing difficulty actually remembering symptom levels beyond the past several days.” Exceptions will be on Day 1 for both the initial and crossover treatments because at these time points, the interest is in subjects’ experiences subsequent to the treatment and not prior to the intervention. During these two days, subjects will be instructed to respond for the period of time since their treatment.

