### 9.4.5 BASELINE DESCRIPTIVE STATISTICS

Balance on baseline covariates will be assessed using absolute standardized difference (ASD) i.e., difference in means or proportions divided by the standard deviation.  $ASD > 0.1$  will be considered to indicate imbalance, and these variables will be adjusted for in the statistical analyses. Analyses will be carried out using modified intention-to-treat i.e., patients who received any study treatment will be analyzed according to the group they were randomized to.

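### The primary analysis pairs tests that cannot adjust with an adjustment rule that will nearly always fire, and plans no between-arm estimate or interval

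*Combined protocol and SAP*

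**What the plan says.** The endpoint is a change score. Section 4.1 says "The primary outcome measure is the change in the phantom limb pain intensity from baseline 1 month following the procedure", and Section 8.1 says "The primary end point will be the difference in average daily phantom pain intensity at baseline and 1 month following the initial intervention", with the average-pain item designated as primary. Section 8.1 makes the comparison between arms: "The primary analyses will compare the two treatments (inter-subject comparisons) during the initial treatment period".

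The test comes from Section 9.1: "Comparisons of independent samples will be performed using Student's t-test for parametric continuous variables or Mann-Whitney U test for nonparametric or categorical variables". A P value below 0.05 "will be considered statistically significant for the primary outcome". The same section summarizes normal data as mean and SD, and other data as median with 10th and 90th percentiles. Sections 9.4.1 and 9.4.2 only refer back to it.

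Adjustment appears once, in Section 9.4.5. An ASD above 0.1 "will be considered to indicate imbalance, and these variables will be adjusted for in the statistical analyses". That section also sets the modified intention-to-treat population.

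The purpose is given in the Synopsis: to "demonstrate feasibility and estimate the treatment effect of using cryoanalgesia", so that a later trial can be sized. Section 9.2 describes the 20 participants as a convenience sample. Section 3 words the primary endpoint as a fall within the treated arm: "limb pain intensity will be significantly decreased relative to baseline pain 1 month following a cryoneurolysis procedure".

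**The concern.** Sections 9.1 and 9.4.5 cannot be carried out together. A two-sample t-test and a Mann-Whitney test have no place for a covariate, so as soon as one variable passes the ASD threshold the analyst must pick a model that the plan does not name, with the data already in view.

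The planned output also does not match the purpose. A later trial is sized from a mean difference and an SD. The plan promises a P value and per-arm summaries. If the Mann-Whitney route is taken, the median and percentile summary supplies neither quantity. The one number the pilot is meant to hand on would then depend on a choice made after the data are seen, or would be missing.

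**Working it through.** **Plan's own figure.** There is no power calculation to reproduce. Sections 5 and 9.3 add 5 to 20 to reach 25, an allowance of 5/25 = 20%, which is consistent.

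**How often the ASD rule fires.** Inputs: 20 analysed (Section 9.2) and 1:1 allocation (Section 6.1.1), so 10 per arm. For a continuous covariate under randomization, the ASD divided by √(2/10) follows a t distribution with 18 df.

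- 0.1 / √0.2 = 0.224, and P(|t₁₈| > 0.224) = 0.826, or about 83%.
- With 12 per arm it is 81%.
- Section 8.1 lists 26 demographic and amputation items (14 + 12), before pain scores. Not all would be usable covariates. If 20 were, 20 × 0.826 = 16.5 would be expected to trigger. With an intercept and an arm term, that leaves 20 − 2 − 16.5 = 1.5 residual df.

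**What a prespecified ANCOVA gains.** Assumptions, because the documents give none: SD at each visit, correlation r between baseline and Month 1, and a two-sided 95% level.

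- Change-score variance: s_b² + s_f² − 2·r·s_b·s_f, where s_b is the baseline SD and s_f the follow-up SD.
- ANCOVA residual variance: s_f²(1 − r²).
- Small-sample cost of estimating the slope: factor 1 + 1/16 on the ANCOVA variance, and 17 rather than 18 df. Together these multiply the variance ratio by (2.101/2.110)² / 1.0625 = 0.933.

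Gain in equivalent sample size = (change variance / ANCOVA variance) × 0.933 − 1, with follow-up SD 2.5:

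| Baseline SD | r = 0.3 | r = 0.5 | r = 0.7 |
|---|---|---|---|
| 2.5 | 8.75/5.69: +44% | 6.25/4.69: +24% | 3.75/3.19: +10% |
| 2.0 | 7.25/5.69: +19% | 5.25/4.69: +5% | 3.25/3.19: −5% |
| 1.5 | 6.25/5.69: +3% | 4.75/4.69: −5% | 3.25/3.19: −5% |

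By simulation with both SDs 2.5, the mean 95% CI half-width falls from about 2.74/2.31/1.79 to 2.28/2.07/1.70 NRS points. Squared ratios are 1.44, 1.25 and 1.11, hence roughly 45%, 25% and 10%. With both SDs 2.0, half-widths computed at the true SD fall from 2.22/1.88/1.46 to 1.86/1.68/1.39.

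**Effect of choosing the test by data shape.** Simulated on rounded 0-10 scores (mean 6, SD 2, 10 per arm, 6,000 trials per setting), with a Shapiro check as an assumed deciding rule. Type I error was 4.7% to 5.7%. The two tests disagreed on significance in about 1.5% of null trials and in 5% to 7% of trials with an assumed 2-point effect.

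**The case against.** The best defence is that this is a declared pilot with every analysis exploratory (Section 9.4.9), that the plan does use baseline, and that it does promise adjustment. Much of that stands, and it rules out several stronger readings.

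- **That the analysis is simply unadjusted.** Section 9.4.5 says otherwise, and if baseline pain counts as a covariate it would usually be adjusted for. The defect is that the named tests cannot do it.
- **That the baseline score is thrown away.** A change score uses it, only less efficiently than ANCOVA in most of the settings above.
- **That chance imbalance leaves the change score badly biased.** A large imbalance would trip the rule. At the threshold itself, with SD 2.5 and r = 0.5, the shift is 0.1 × 2.5 × (1 − 0.5) = 0.125 points.
- **That switching tests inflates false positives.** The simulation shows error near nominal. Section 9.1 also states no normality check, so selection on observed shape is a plausible reading and not a stated rule.
- **That a placebo response could satisfy the primary analysis.** Sections 6.1.1 and 8.1 make it a parallel-group comparison. The within-arm phrasing in Hypothesis 1 and Section 3 is a wording mismatch.
- **That the wide uncertainty in an SD from 20 people counts against these tests.** It comes from the sample size, and ANCOVA would not remove it.

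On the t-test route a reader could also derive a difference and interval from the two means and SDs. But the plan does not commit to that route. Exploratory status makes an estimate with an interval more fitting than a significance verdict.

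**Conclusion.** The concern holds in a limited form. Sections 9.1 and 9.4.5 are not executable together, and no model, between-arm effect measure or interval is named for a pilot whose purpose is estimation. The 83% trigger rate needs only randomization, 10 per arm and an approximately normal covariate. The precision gain rests on assumed SDs and correlations: roughly 45% to 10% more participants' worth if SDs are equal, down to about −5% if the baseline SD is much the smaller. The inclusion threshold of NRS 4 or higher makes a narrower baseline spread plausible. The case for the change therefore rests first on having one defined, executable estimate, and second on precision. It should be made before analysis, but it does not put the trial's conduct in question.

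**What to change.** State one primary analysis: ANCOVA of Month-1 average phantom NRS on arm plus baseline average phantom NRS, in the modified intention-to-treat set. Report the adjusted active-minus-sham difference with its 95% CI as the primary result, and give the residual SD for planning. Keep the Mann-Whitney test on change as a sensitivity analysis only. Replace the ASD > 0.1 trigger with this single prespecified covariate; ASDs can still be tabulated descriptively. Reword Hypothesis 1 and the Section 3 primary endpoint as between-arm differences, to match Section 8.1.

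Both scores are already collected under the Section 8.1 schedule, so the cost is wording and one degree of freedom.

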#### 9.2 SAMPLE SIZE DETERMINATION

This is a pilot study to assist in powering a subsequent definitive trial and we therefore use a convenience sample of 20 participants.

#### 9.3 POPULATIONS FOR ANALYSES

A total of 20 individuals are anticipated for the analysis. However, will are requesting an additional 5 permitted to account for dropouts. This will total up to 25 participants.

## 9.4 STATISTICAL ANALYSES

### 9.4.1 GENERAL APPROACH

Please see above.

### 9.4.2 ANALYSIS OF THE PRIMARY EFFICACY ENDPOINT(S)

Please see above.

### 9.4.3 ANALYSIS OF THE SECONDARY ENDPOINT(S)

Please see above and as follows.

### 9.4.4 SAFETY ANALYSES

**Complications.** The investigators will record all related complications (all are extraordinarily rare). These complications cannot be “ranked”, but rather the two groups will be compared descriptively on each of these possible complications.

### 9.4.5 BASELINE DESCRIPTIVE STATISTICS

Balance on baseline covariates will be assessed using absolute standardized difference (ASD) i.e., difference in means or proportions divided by the standard deviation.  $ASD > 0.1$  will be considered to indicate imbalance, and these variables will be adjusted for in the statistical analyses. Analyses will be carried out using modified intention-to-treat i.e., patients who received any study treatment will be analyzed according to the group they were randomized to.

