# 6 STUDY INTERVENTION

## 6.1 STUDY INTERVENTION(S) ADMINISTRATION

### 6.1.1 STUDY INTERVENTION DESCRIPTION

For individuals of childbearing potential, a sample of urine will be collected before any study interventions to confirm a non-pregnant state.

**Treatment group allocation (randomization).** Participants will be allocated to one of two possible treatments groups:

1. *Cryoneurolysis*
2. *Sham procedure (Control)*

Randomization lists will be created using computer-generated tables by the Investigational Pharmacy (UC San Diego) in a 1:1 ratio and block sizes of 2. Treatment group assignment will be conveyed to the investigators in the form of sealed, opaque envelopes only by the treating investigator. Therefore, all investigators and participants will be masked to treatment group assignment, with the only exception being the investigator who performs the procedure (and will not have subsequent contact with the participant). ***This protocol will enable a randomized, observer- and participant-masked, sham/placebo-controlled study.*** It is impossible to mask the individual performing the cryoneurolysis procedure because the ice ball forming at the distal end of the probe—with *active* treatment—is clearly visible by ultrasound; and the lack of an ice ball for placebo participants is equally clear. It is essential to continuously visualize the probe and target nerve throughout the two freeze/thaw cycles to ensure the entire nerve diameter is adequately treated and remains relatively motionless. This cannot be achieved if the ultrasound is turned off during nitrous oxide administration to mask the provider; and we prioritize patient safety over masking of the physician administering the intervention. All participants will have a peripheral intravenous (IV) catheter inserted, standard noninvasive monitors applied (blood pressure cuff, pulse oximeter, 5-lead ECG), and oxygen administered *via* a nasal cannula or facemask. Midazolam and fentanyl (IV) will be titrated for patient comfort, while ensuring that patients remain responsive to verbal cues.

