**Table 1. Summary of post-enrollment assessments.**

Subjects:	All							Participating in Crossover *							All
Time Point Following:	Initial Treatment							Crossover Treatment							Initial
Time Point (Days):	0	1	7					0	1	7					
Time Point (Months):				1	2	3	4				1	2	3	4	12
Phantom Limb Pain (worst, least, average, current), NRS	•	•	•	•	•	•	•	•	•	•	•	•	•	•	•
Residual Limb Pain (worst, least, average, current), NRS	•	•	•	•	•	•	•	•	•	•	•	•	•	•	•
Patient Global Impression of Change Scale		•	•	•	•	•	•		•	•	•	•	•	•	•
Brief Pain Inventory Interference Scale	•	•	•	•	•	•	•	•	•	•	•	•	•	•	•
Non-Painful Phantom Sensations (# and duration)	•	•	•	•	•	•	•	•	•	•	•	•	•	•	•
Phantom Limb Pain (# and duration)	•	•	•	•	•	•	•	•	•	•	•	•	•	•	•
Residual Limb Pain (# and duration)	•	•	•	•	•	•	•	•	•	•	•	•	•	•	•

\* The “crossover” treatment intervention will occur 4-6 months following the initial treatment

**Demographic and amputation history.** Subjects will have demographic and anthropomorphic data collected including age, sex, gender, height, weight, years of educational, employment status, marital status, military status, race, ethnicity, current analgesic regimen (including adjuvants such as acupuncture), comorbidities, and any chronic pain other than study limb including location and details. In addition, amputation-specific data will include side of amputation, anatomic location of amputation, contralateral amputation, years since initial amputation, time since phantom pain began, phantom pain description, time since residual pain began, date(s) of subsequent surgical procedures, amputation etiology, amputation level, other amputations (with dates/etiology/pain), and prosthesis use. Immediately prior to premedication the phantom and residual limb pain intensities will be record. Immediately prior to and then following the treatment of each peripheral nerve we will collect the phantom pain score, residual pain score, the treatment point from distal end of limb, duration of argon treatment, and the highest pain during the treatment. We will also note and describe any protocol deviations and adverse events.

All remaining data collection following the day of the intervention (Day 0) will be collected by telephone from the University of California San Diego by the investigators, Program Manager, and/or research coordinators specifically trained in these instruments’ application, minimizing inter-rater discordance

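### The rule to adjust for every baseline variable with ASD > 0.1 flags about four in five continuous or common binary variables by chance at this sample size, with no covariate list, cap or model, and conflicts with the unadjusted tests in 9.1

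*Combined protocol and SAP*

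**What the plan says.** Section 9.4.5 defines the ASD as the "difference in means or proportions divided by the standard deviation" and states that a value above 0.1 "will be considered to indicate imbalance, and these variables will be adjusted for in the statistical analyses". It does not say which variables enter the check, how many may be adjusted for, which model carries the adjustment, or which analyses are meant.

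Section 9.1 names the tests: "Comparisons of independent samples will be performed using Student's t-test for parametric continuous variables or Mann-Whitney U test", with chi-square or Fisher's exact test for proportions. It sets P < 0.05 for the primary outcome. Sections 9.4.1 and 9.4.2 only refer the reader to what stands above them.

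On size, 9.2 says "we therefore use a convenience sample of 20 participants", and 9.3 adds up to five for dropouts: "This will total up to 25 participants". Section 6.1.1 randomizes "in a 1:1 ratio and block sizes of 2".

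The only list of baseline variables is in 8.1, in the paragraph on demographic and amputation history. It begins with "age, sex, gender, height, weight, years of educational, employment status, marital status, military status, race, ethnicity" and continues: "In addition, amputation-specific data will include side of amputation, anatomic location of amputation, contralateral amputation, years since initial amputation", and further items.

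**The concern.** A cut-off of 0.1 suits large studies, where a difference of that size is unlikely to arise by chance. In a randomized trial with 10 per arm, differences of that size are the rule even when randomization has worked perfectly. A mandatory instruction to adjust for all of them would load the model with covariates picked by noise.

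The stated purpose of the pilot is to estimate the treatment effect and help size a definitive trial. Two things are at stake for the adjusted estimate. It may be much less precise than a simple comparison, or impossible to compute. And because the plan leaves the variables and the model open, whoever runs the analysis must choose them after seeing the data.

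**Working it through.** The plan gives no effect size, SD or power for its 20 participants and no expected flag rate for the 0.1 cut-off, so it has no figure of its own to reproduce.

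**Inputs from the documents.** 20 analysed (9.2) at 1:1 (6.1.1) gives 10 per arm. If all 25 are analysed (9.3), the arms are 12 and 13. The cut-off is 0.1 (9.4.5). Section 8.1 lists 14 demographic and clinical items and 12 amputation items, so 26, before the baseline pain scores are counted.

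**Step 1: chance flag rate, continuous variable.** Under randomization, ASD = |t| × √(1/n₁ + 1/n₂).
- 10 per arm: 0.1/√(2/10) = 0.224, and P(|t₁₈| > 0.224) = 0.826.
- 12 and 13 per arm: 0.1/√(1/12 + 1/13) = 0.250, and P(|t₂₃| > 0.250) = 0.805.

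For scale, a cut-off of 0.1 would flag 5% of variables by chance only at about 769 per arm.

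**Step 2: chance flag rate, binary variable, 10 per arm.** A difference of one participant is 0.1 in proportion. The SD of a binary variable is at most 0.5, so the ASD is at least 0.1/0.5 = 0.2. Anything short of exact equality is flagged. The flag rate is therefore 1 minus the probability that two binomial(10, p) counts agree: 0.69 at p = 0.1, 0.78 at 0.2, 0.81 at 0.3, 0.82 at 0.5. Rarer traits are flagged less often (0.54 at p = 0.05).

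**Step 3: if all 26 items were checked.** The model with intercept and treatment leaves N − 2 degrees of freedom. It cannot be estimated once the number of single-df covariates reaches that figure. Each item is treated here as one independent variable with the continuous flag rate.
- 20 analysed: 26 × 0.826 = 21.5 flagged on average, against 18 df. P(18 or more flagged) = 0.97.
- 25 analysed: 26 × 0.805 = 20.9 flagged, against 23 df. P(23 or more flagged) = 0.22.

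With an assumed mix of 8 continuous and 18 binary items and 20 analysed, 79.5% are flagged and the model is not estimable in 93% of simulated trials.

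**Step 4: if a shorter list were checked (20 analysed).** For k covariates unrelated to outcome, the variance of the treatment coefficient rises by about (N − 3)/(N − 3 − k) = 17/(17 − k). It doubles at about nine adjusted covariates (17/8 = 2.1), which is about 11 candidates (9/0.826 = 10.9). Simulation applying the ASD rule, 4,000 runs for each row, with an assumed SD of 2.5 NRS points and covariates unrelated to outcome:

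| Candidates checked | Mean number adjusted for | Median variance ratio | Median 95% CI half-width (NRS points) |
|---|---|---|---|
| none | 0 | 1.0 | 2.3 |
| 5 | 4.1 | 1.3 | 2.7 |
| 8 | 6.6 | 1.6 | 3.1 |
| 15 | 12.4 | 3.5 | 4.9 |

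**Step 5: the tests.** The t-test, Mann-Whitney, chi-square and Fisher tests in 9.1 have no place for a covariate. The adjustment required by 9.4.5 needs a regression model, and none is named anywhere. This holds whatever the number of variables checked.

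**The case against.** Several points on the other side are sound.

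- **The 26 items are a data-collection list.** Nothing says that all of them enter the ASD check. Some, such as the description of phantom pain or the dates of later surgery, are not single variables with a mean or proportion, and amputation level has little room to vary when only trans-femoral amputees are eligible. Against that, items with several levels, such as race and etiology, would use more than one df each. The 97% is therefore conditional on a reading that the plan neither states nor rules out.
- **The sample may reach 25.** Estimation then fails far less often, as Step 3 shows.
- **Prognostic covariates would offset part of the loss.** If one of the adjusted covariates correlates 0.5 with the outcome, the variance ratio is 0.75 × 17/(17 − k): 1.06 with five adjusted and 1.42 with eight. At a correlation of 0.7 the loss is wholly offset (0.51 × 17/12 = 0.72 and 0.51 × 17/9 = 0.96). But adjusting for that one covariate alone does better: 0.75 × 17/16 = 0.80 and 0.51 × 17/16 = 0.54. The rule would also leave out such a covariate whenever it happens to look balanced, about 17% of the time (1 − 0.826).
- **The rule may not govern the primary analysis.** It stands under baseline descriptive statistics, and 9.4.2 points back to unadjusted tests. An unadjusted primary analysis is a possible reading. But 9.4.5 refers to the statistical analyses in general and exempts none.
- **This is a pilot.** Section 9.4.9 calls all analyses exploratory. Section 9.1 nevertheless keeps a significance threshold for the primary outcome, and the effect estimate is a stated aim.

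A reader might infer that the adjusted analysis is bound either to fail or to lose most of its precision. The documents do not support that: with 5 or 8 candidates the model fits, and at 8 about 60% of the precision remains (1/1.6). A reader might also infer that the pilot could not supply a variance for the next trial. It can: 9.1 reports normally distributed data as mean and SD, and no adjustment rule alters the SD of NRS change.

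**Conclusion.** The concern holds in conditional form. Three parts do not depend on how many variables are checked: a 0.1 cut-off treats ordinary chance differences as imbalance in about four of five continuous or common binary variables; the rule has no list, cap or model; and the tests in 9.1 cannot carry it out. As written, the plan does not settle which analysis gives the primary result, and any adjusted effect estimate would rest on choices made after the data are seen.

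The size of the harm does depend on that number. It runs from a modest widening of the interval with about five candidates to an inestimable model in most cases if the whole of 8.1 is used with 20 analysed. The half-widths rest on the assumed SD of 2.5 and on covariates unrelated to outcome. The working shows imprecision and discretion, not systematic bias in the estimate.

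**What to change.** In 9.4.5, delete the 0.1 imbalance trigger and the clause requiring adjustment for flagged variables. Report ASDs in the baseline table as description only.

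In 9.1 or 9.4.2, name the primary analysis: a linear model (ANCOVA) of the 1-month average phantom-pain NRS on treatment, with baseline average phantom-pain NRS as the single pre-specified covariate. With baseline in the model, the treatment coefficient is the same whether the outcome is the 1-month score or the change from baseline, so the endpoint in 8.1 is respected. Any further covariate should be named in advance and used only in a sensitivity analysis. Removing the trigger without naming the model would leave the primary analysis to be inferred from the general list of tests in 9.1.

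The cost is a few sentences of wording and one degree of freedom. No new data are needed, since 8.1 already collects baseline phantom pain.
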